11.4 Institutional Review Board (IRB) Review and Informed Consent

This protocol, the informed assent/consent documents, and any subsequent modifications will be reviewed and approved by the UNC IRB who is responsible for the oversight of the study. The informed assent/consent will describe the purpose of the study, the procedures to be followed, and the risks and benefits of participation.

Consent/assent will be obtained to explain the nature, significance, and risks of the study. Sample informed consent/assent forms are included.

11.5 Waiver of the Requirement for Parental Permission for Special Circumstances

The site IRBs and the UNC IRB as the central IRB will be requested to grant a waiver of parental permission to participate in this research study for youth participants under (not inclusive of) the age of 18.

Under 45 CFR 46.408 (c), an IRB has the authority to waive parental permission if it determines that “a research protocol is designed for conditions or a subject population for which parental or guardian permission is not a reasonable requirement to protect the subjects” and “an appropriate mechanism for protecting the children who will participate as research subjects is substituted” and “that the waiver is not inconsistent with Federal, State, or local law.”

A request for a waiver of the requirement for parental permission is requested for 2 reasons: 1) many youth would be reluctant to participate in this study – which focuses on HIV and risks for poorer medication adherence – if they are required to get parental permission; and 2) many of the youth in our study are likely to be gay, bisexual, or have an attraction to persons of the same gender, but may not be out to their parents; requiring parental permission may place participants at risk for outing themselves as part of the LGBT community or having HIV. For these reasons, we believe it is important to be granted a waiver for parental permission for this study population.

11.6 Waiver of the Requirement for Signed Consent Form

11.6.1 For Eligibility Screening

An online consent process for the eligibility screening is proposed. The introduction to the screening interview includes all the required elements for consent (45 CFR 46.116). No identifying information on volunteers is recorded during the online screening until a participant is determined eligible (i.e., by marking “I do consent to be screened for eligibility”). Therefore, there will be no identifying link of who agreed to be screened or not screened for the study. In addition, the screening presents minimal risk to participants and involves no procedures that would require written consent outside of a research context. Under these conditions the IRB is authorized to modify the requirements to obtain a signed consent form for some or all subjects (45 CFR 46.117 [c]).

11.7 Prisoner Participation

NICHD has concluded that this protocol does NOT meet Federal requirements governing prisoner participation in human subjects research and should NOT be considered by local IRBs for the recruitment of prisoners. Subjects enrolled who subsequently become incarcerated or are placed in detention may not continue study participation. Study visits cannot be conducted during the period of incarceration or detention.

11.8 45 CFR Parts 160 and 164 Standards for Privacy of Individually Identifiable Health Information ("Privacy Rule" Pursuant to the Health Insurance Portability and Accountability Act - HIPAA)

Each site is responsible for adherence to their individual institution's HIPAA policies and procedures.

11.9 Study Discontinuation

This study may be discontinued at any time by the UNC IRB, NICHD, or other government agencies as part of their duties to ensure that research participants are protected.

12.0 PUBLICATION OF RESEARCH FINDINGS

Any presentation, abstract, or manuscript will be made available for review by the study sponsor(s) prior to submission.

# 1 Revision History

Version	Date	Summary of Changes
Final	05-JAN-2022	
Amendment 1	07-JULY-2022	
Minor Changes Throughout: Updates to notation to maintain consistency. Also added/removed and changed sentences as necessary to improve the organization of the protocol.
 
Section 3.1 (see also Table 4, 8, and 10)

	04-MARCH-2022	Changed the primary study objective to consider FTC-tp and TFV-dp levels in the blood separately.
	28-JAN-2022	
Section 3.2 (see also Tables 5, 6, 8, and 12)
 Removed secondary objective II, where FTC-tp and TFV-dp were analyzed as continuous outcomes.
	13-APR-2022	Added self-reported weekly and monthly PrEP use as outcomes of interest for the secondary study objective.
	10-JAN-2022	Added exploratory outcomes as determined by the study team.
	10-JULY-2022	
Section 3.3 (see Table 6)
 Updated the cost effectiveness objective to reflect that it is a comparison between P3 and P3+ as originally defined in the protocol.
	09-MARCH-2022	
Section 4.2 (see Table 7)
 Updated super learner libraries. We added a simple model and regularization models (glmnet and stepwise selection) out of concern regarding the large number of confounders in our models.

	26-JUNE-2022	Removed statement regarding double robustness of TMLE.
	13-APR-2022	Added race/ethnicity to the variable list.  Section 4.3 (see also Table 8)
	13-APRIL-2022	Hypothesis testing for 3 and 6 months was separated into two different hypothesis tests as opposed to considering a joint test of no treatment effect at both 3 and 6 months. This effects the primary and secondary/exploratory objectives.  Section 4.4
	13-JULY-2022	Added this section to explain cost analysis.  Section 6.1
	25-JUNE-2022	Timeline updated to reflect realized dates  Section 6.2
	16-MARCH-2022	Updated the imputation steps for missing survey data.  Section 6.3
	13-APR-2022	Race/ethnicity was added as a confounder to control for in all analyses (see also Table 7).  Section 6.4
	21-JUNE-2022	Removed longitudinal TMLE as a sensitivity analysis for unmeasured, time-varying confounding.  Supplement
	09-MARCH-2022	Added a sensitivity analysis for the primary objective.
	21-JUNE-2022	Rewrote the supplement to provide adequate detail regarding the TMLE procedure for incorporating survey data into the analysis of the primary objective.

# Contents

1 Revision History	1
2 Abbreviations and Definitions	4
3 Study Objectives	4
3.1 Primary Study Objectives . . . . .	4
3.2 Secondary Study Objectives . . . . .	4
3.3 Cost Effectiveness Objectives . . . . .	4
4 Analysis Plan	5
4.1 Notation and Causal Estimands . . . . .	5
4.2 TMLE Analysis for Average Causal Effects . . . . .	6
4.3 Hypothesis Tests and Multiple Testing Adjustment . . . . .	7
4.4 Cost Analysis . . . . .	7
5 Reporting Results	9
5.1 Initial Descriptive Statistics and Data Exploration . . . . .	9
5.2 Primary and Secondary Analysis Results . . . . .	9
6 General Considerations and Statistical Issues	10
6.1 Timeline . . . . .	10
6.2 Missing Data and Modification of Primary Analysis . . . . .	12
6.3 Confounder Selection . . . . .	13
6.4 Definition of the Primary Outcome . . . . .	13
A Supplement	13
A.1 G-Formula for causal estimands of interest . . . . .	13
A.2 Causal Assumptions . . . . .	13
A.3 Super Learning and TMLE Parameters . . . . .	14
A.4 Variance Estimation . . . . .	14
A.5 Incorporating Survey Data into the Primary Analysis . . . . .	14
A.5.1 Notation . . . . .	14
A.5.2 New Estimand . . . . .	14
A.5.3 Efficient Influence Curve of the Estimand . . . . .	15
A.5.4 Implementation Steps . . . . .	15
A.5.5 Additional Causal Assumptions . . . . .	16
B References	16

Table 4: Primary outcome measures of interest.

Outcome	Definition(s)	Collection Method
Protective level of TFV-dp in the blood	TFV-dp levels in the blood consistent with PrEP use >4 days per week	DBS
Protective level of FTC-tp in the blood	FTC-tp levels in the blood consistent with PrEP use >4 days per week	DBS

## 2 Abbreviations and Definitions

CASI - Computer-assisted self-interviewing

DBS - Dry blood spot

SOC - Standard of care

STI - Sexually transmitted infection

TMLE - Doubly robust targeted minimum-loss based estimation

## 3 Study Objectives

### 3.1 Primary Study Objectives

The primary objective of this analysis is to assess the efficacy of P3/P3+ at improving PrEP adherence, as compared to Standard of Care (SOC), at both 3 months and 6 months of follow-up. The primary outcomes of interest will be a protective level of TFV-dp and FTC-tp in dry blood spot (DBS) plasma. These two measures will be analyzed separately for the primary objective.

### 3.2 Secondary Study Objectives

As detailed in the study protocol, the secondary objectives of this analysis are as follows:

1. Replicate the primary objectives with P3 and P3+ considered separately against the SOC group (i.e. P3 vs. SOC and P3+ vs SOC).
2. Analyze the effect of the intervention on self-reported weekly PrEP use and self-reported monthly PrEP use.
3. Analyze the effect of intervention on a panel of self-reported outcomes which include, PrEP retention and persistence, PrEP clinical care, sexual risk, and incident sexually transmitted infection (STI).

The outcomes for secondary objective one are the same as the primary outcome and are listed in table 4. Table 5 lists outcomes for secondary objectives two and three. These outcomes will be assessed at both the 3 month time point and the 6 month time point.

### 3.3 Cost Effectiveness Objectives

The last objective of the study is to assess the cost effectiveness of P3+ compared to P3. We will compare cost effectiveness of interventions by calculating  $\Delta C/\Delta E$ , where  $\Delta C$  is the difference in mean costs of the intervention and  $\Delta E$  is the mean difference in the effectiveness.

Table 5: Secondary Objective Outcomes

Outcome	Definition	Collection Method
TFV-dp	Same as primary objective	DBS
FTC-tp	Same as primary objective	DBS
Weekly PrEP Use	Self-reported number of days in the past week that the patient took their PrEP medication	CASI
Monthly PrEP Use	Self-reported percent of time in the past month that the patient took PrEP as prescribed	CASI
Incident Sexually Transmitted Infections (STI): gonorrhea, chlamydia, and syphilis	Self-reported diagnosis of the STI in the past 3 months	CASI
Persistence	Reporting currently taking PrEP	CASI
Retention	Patient attended at least one routine/scheduled PrEP visit in the past 3 months	CASI
Sexual Risk	Self-reported number of times receptive condomless anal sex in the past 3 months Self-reported number of times insertive condomless anal sex in the past 3 months	CASI CASI

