ATN	Adolescent Medicine Trials Network for HIV/AIDS Interventions
CASI	Computer assisted self-interview
CFR	Code of Federal Regulations
CRF	Case report form
DBS	Dried blood spot
DHHS	U.S. Department of Health and Human Services
FTC-TP	Emtricitabine Triphosphate
GCP	Good Clinical Practices
HIV	Human Immunodeficiency Virus
IRB	Institutional Review Board
MC	Management Core
MSM	Man who has sex with men or men who have sex with men
NICHD	National Institute of Child Health and Development
NIDA	National Institute on Drug Abuse
NIH	National Institutes of Health
NSC	Next Step Counseling
P3	Prepared, Protected, EmPowered
PrEP	Pre-exposure prophylaxis
PI	Principal Investigator
OHRP	Office of Human Research Protection
QNS	Query and Notification System
RCT	Randomized controlled trial
SID	Study ID number
SMART	Study Management and Retention Tool
SRV	Subject Recruitment Venue
SSL	Secure Socket Layer
TAF	Tenofovir Alafenamide
TFV-DP	Tenofovir Diphosphate
TC	Technology Core
TW	Transgender women
TWSM	Transgender woman who has sex with men
YAB	Youth Advisory Board
YMSM	Young men who have sex with men
YTWSM	Young transgender women who have sex with men

STUDY ABSTRACT

DESIGN:	This study is a three arm, randomized-controlled trial (RCT) that will test the efficacy of P3, a novel, theory-based mobile app that utilizes game mechanics and social networking features to improve PrEP adherence, retention in PrEP clinical care, and PrEP persistence among young men who have sex with men (YMSM) and young transgender women who have sex with men (YTWSM), ages 16-24. We will test the efficacy of P3 and P3+, which adds Next Step Counseling delivered by an adherence counselor through the app, against PrEP standard of care. Participants will be randomized to P3, P3+, or standard of care. The study will evaluate the efficacy of P3, P3+. A cost comparison between P3 and P3+ will be conducted.
DURATION:	The total duration of study participation for each RCT subject is 6 months. The duration of the P3 intervention arms is 3 months.

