2.2 Secondary Objective

Secondary objectives include testing the efficacy of P3 and P3+ in terms of the primary outcomes above, but with the interventions considered separately against standard of care. We will also assess differences between P3/P3+ versus standard of care in terms of self-reported weekly PrEP use and self-reported monthly PrEP use to see if these results align with the primary results. Additional secondary outcomes of interest for P3/P3+ include self-reported retention in PrEP clinical care, PrEP persistence, sexual risk behaviors, and (self-reported) STI incidence.

A cost comparison between P3 and P3+ will be conducted to assess the incremental cost effectiveness ratio across intervention arms.

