4.0 SELECTION AND ENROLLMENT OF ALL STUDY PARTICIPANTS

4.1 Inclusion Criteria for all phases

- Ages 16-24, inclusive
- Male sex at birth
- Report sex with men
- Able to speak and read English
- HIV-negative (self-report)

Additional inclusion criteria for usability testing

- Familiarity with an Android or iOS smartphone
- Have previously taken, are currently taking or considering taking PrEP
- Recruited from one of 2 iTech SRV cities (Boston, Massachusetts; Chicago, Illinois)
- Ability to attend usability session on dates specified by the research team

Additional inclusion criteria for field testing

- Reliable daily access to Android or iOS smartphone with a data plan
- Initiated PrEP within the last 60 days and have an active PrEP prescription (prescription confirmed by study staff) OR on PrEP >60 days but self-report adherence on average < 6 pills

per week over the past month and have an active PrEP prescription (prescription confirmed by study staff)

- Recruited from one of 3 iTech SRV cities for field testing (Bronx, New York; Houston, Texas; Philadelphia, Pennsylvania)
- Willing to adhere to study collection of whole blood and hair specimens.

Additional inclusion criteria for RCT

- Reliable daily access to Android or iOS smartphone with a data plan
- Willing to download video teleconferencing application, such as Zoom
- Not currently on PrEP but plan to initiate in the next 7 days and have an active PrEP prescription (prescription confirmed by study staff) OR on PrEP and have an active PrEP prescription (prescription confirmed by study staff)
- Recruited from one of 9 iTech SRV cities for RCT (Atlanta, Georgia; Boston, Massachusetts; Bronx, New York; Chapel Hill, North Carolina; Charlotte, North Carolina; Chicago, Illinois; Houston, Texas; Philadelphia, Pennsylvania; Tampa, Florida)
- Willing to adhere to study collection of whole blood specimens, including self-collection

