10.3.4 RCT Secondary and Cost Analysis Plan

Secondary Outcomes: We will conduct an analysis parallel to the primary analysis exactly as above, but with the two P3 intervention arms separated (i.e., P3 vs. SOC, P3+ vs. SOC). We will also assess intervention efficacy at improving PrEP adherence by analyzing self-reported PrEP use, namely weekly PrEP use and monthly PrEP use at both 3- and 6- months follow-up. Lastly, for the secondary objective we will consider the effect of P3/P3+ on a panel of self-reported outcomes including: retention in PrEP care, PrEP persistence, sexual risk, and incident STIs. For binary outcomes, we define intervention efficacy as a difference in proportions, while for continuous outcomes, we define efficacy as a difference in means.

Compliance analyses: In addition to the ITT analyses above, we will examine methods that include covariates that quantify the degree of app usage, such as estimating the complier average causal effect of the interventions.

Table 1: Outcomes and Measures

Primary Study Outcomes: To improve PrEP adherence	
PrEP adherence	Whole blood specimen to assess blood plasma and intracellular concentration of TFV-DP or TAF and FTC-TP. We will also assess self-reported PrEP adherence (number of days of last 7 PrEP was taken; % of days PrEP taken in the last month). PrEP adherence $\geq 57\%$ (4 out of 7 doses/week) will be considered “high” adherence, Whereas $< 57\%$ will be considered “low” adherence for the purposes of analyses.
Secondary Study Outcomes: To increase retention in PrEP clinical care, PrEP persistence, and Information, and reduce sexual risk behaviors and STI incidence	
Self-Reported Retention in PrEP Clinical Care	Self-reported adherence to PrEP medical care visits in the previous 3 months.
PrEP Persistence	Duration of PrEP use before an individual discontinues either temporarily or permanently. This will be collected via self-report at follow-up.

Sexual Risk Behaviors	Sexual Practices Assessment Schedule will be adapted to explore the number of occasions of different sexual acts (anal: receptive, insertive), with three different types of partners (romantic interest, casual partner “hookup”, or transactional). ⁴⁵
STI Incidence	Self-reported STIs (e.g., rectal and urethral gonorrhea and chlamydia, syphilis) in last 3 months
Potential Confounders and Effect Modifiers	

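### The SAP analyses PrEP persistence as current use at the visit, while the protocol defines it as duration of use until any stop; the change is unrecorded, so the result should not be reported as persistence

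*SAP*

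**What the plan says.** Persistence is part of the trial's stated purpose. The protocol's abstract presents an app meant to "improve PrEP adherence, retention in PrEP clinical care, and PrEP persistence among young men" who have sex with men, and young transgender women. Protocol section 2.2 names it as a secondary outcome: "Additional secondary outcomes of interest for P3/P3+ include self-reported retention in PrEP clinical care, PrEP persistence, sexual risk behaviors, and (self-reported) STI incidence".

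The protocol defines it in section 10.3.4, Table 1: "Duration of PrEP use before an individual discontinues either temporarily or permanently. This will be collected via self-report at follow-up". The same section sets the effect measures: "For binary outcomes, we define intervention efficacy as a difference in proportions, while for continuous outcomes, we define efficacy as a difference in means".

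SAP section 3.2 presents its secondary objectives as those of the protocol and places persistence in the self-reported panel of the third one. SAP Table 5 then defines persistence, collected by computer-assisted self-interview, as "Reporting currently taking PrEP". On timing, section 3.2 says: "These outcomes will be assessed at both the 3 month time point and the 6 month time point". SAP section 4 estimates binary outcomes as proportions. Nothing in the SAP analyses duration of use, time to stopping or gaps in use. The revision history logs the addition of exploratory outcomes but no change to the definition of persistence.

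**The concern.** The two documents use one name for two outcomes. The protocol describes a history that any stop ends, including a temporary one. The SAP records a status on the day of the survey, which cannot show a temporary stop that is already over.

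If the SAP analysis is reported under the name persistence, a difference between arms will be read as a difference in sustained use. The analysis would show only that more people in one arm were taking PrEP when asked. Sustained use is one of three things that the app is meant to improve, and no other analysis in the SAP measures it over the full interval between visits.

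**Working it through.** The documents state no rate, effect or power for persistence, so there is no figure to reproduce. The check sets the two definitions side by side for the four possible patterns of use up to a visit.

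- **Uninterrupted use.** Protocol: duration still running. SAP: persistent. They agree.
- **Stopped, back on PrEP at the visit.** Protocol: duration ended at the stop. SAP: persistent. They disagree.
- **Stopped, still off at the visit.** Protocol: duration ended at the stop. SAP: not persistent. They agree on class, although the SAP outcome no longer separates an early stop from a late one.
- **Never started.** Protocol: if scored at all, a duration of zero, the lowest value. SAP: not persistent. They agree.

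So the classification differs for those who stopped and restarted, and always in the same direction: the SAP counts them as persistent. One consequence is that a participant can be non-persistent at month 3 and persistent at month 6 under the SAP. That cannot happen under an outcome that the first stop ends.

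The effect on the comparison between arms depends on rates that the documents do not give. What follows is an illustration in which every rate is assumed. Let *p* be the proportion with uninterrupted use to the visit, and *r* the share of the remainder who are back on PrEP at the visit. Then

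current use = *p* + (1 − *p*)·*r*.

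Take *p* = 0.50 in standard of care and 0.65 in P3/P3+, a difference of 15 points in uninterrupted use.

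- *r* = 0.20 in both arms: 0.50 + 0.50 × 0.20 = 0.60, and 0.65 + 0.35 × 0.20 = 0.72. Difference 12 points.
- *r* = 0.40 in both arms: 0.70 and 0.79. Difference 9 points. With equal *r* the difference shrinks by the factor (1 − *r*).
- *r* = 0.40 in standard of care, 0.20 in P3/P3+: 0.70 and 0.72. Difference 2 points.
- *r* = 0.20 in standard of care, 0.40 in P3/P3+: 0.60 and 0.79. Difference 19 points.

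Now let uninterrupted use be equal, *p* = 0.50 in both arms, with *r* = 0.20 in standard of care and 0.40 in P3/P3+. Current use is 0.60 and 0.70: a 10-point difference in an outcome called persistence, with no difference in uninterrupted use.

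**The case against.** The strongest reply is that the protocol definition could not be run as written. It gives no starting date for people already on PrEP at enrolment, no length of gap that counts as a temporary stop, and no rule for use that continues past month 6. A difference in means does not handle durations cut off at the end of follow-up. The SAP had to choose something, and Table 5 states its choice openly. This is fair as a reason for choosing a workable definition. It does not explain why the chosen definition drops the protocol's rule that a temporary stop ends persistence, or why the change is not recorded.

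A second reply is that self-reported monthly use, analysed under the second secondary objective, would pick up recent gaps. It would, but only within the past month; visits are three months apart.

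A third is that materiality is low. That stands. SAP section 4.3 calls the third secondary objective exploratory and controls the false discovery rate at 0.20.

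A reader might also infer that the SAP is wrong to score never-starters as non-persistent, since the trial admits people described as "Not currently on PrEP but plan to initiate in the next 7 days and have an active PrEP prescription". The documents do not support this. The protocol does not exclude never-starters from the outcome, a duration of zero would also rank them lowest, and section 10.3.4 describes its analyses as intention to treat. Scoring everyone randomised keeps that comparison.

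**Conclusion.** The discrepancy is real and follows from the wording alone. The SAP outcome is the proportion taking PrEP at each visit. It supports a conclusion about current use and none about persistence as the protocol defines it.

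Its size is unknown. The share of participants who change class is the share who stopped and were back on PrEP by the visit, and no document gives that rate. A reader might infer that the SAP definition favours the intervention. The documents do not support a direction: equal restarting in the two arms dilutes a difference, and unequal restarting can shrink, enlarge or create one.

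The point is minor. It affects the label and interpretation of one exploratory-family outcome. The blood-level primary outcomes are unaffected.

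**What to change.** In SAP Table 5 and the Secondary III results table (shell Table 13), rename the outcome as current PrEP use at visit. Record it as a departure from the protocol definition, with the reason, and draw no conclusion about persistence from it. This costs almost nothing.

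Then check what the follow-up surveys asked. Protocol Table 1 says that persistence is collected by self-report at follow-up, but the survey items are not shown, so it is not certain that interim stops or their dates were recorded. If they were, add a supplementary binary outcome, analysed with the same TMLE in all randomised participants: uninterrupted use from baseline, or from first dose for those starting after enrolment, through month 3 and through month 6. State the gap length that counts as a stop. Count never-starters as not persistent; otherwise they have no stop to record and could pass by default, and dropping them would condition on initiation after randomisation. Label the outcome post hoc, because SAP section 6.1 lists the analysis as done on April 20, 2022.

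The cost is one derived variable and one more table row. The variable depends on recall, which is longer for participants who miss month 3 and complete month 6, as protocol section 6.4 allows.
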